#### 5 SAMPLE SIZE AND POWER

Approximately 85 subjects will be enrolled in Phase 1a. In dose escalation, between 3 and 9 subjects are expected to be treated at each dose escalation cohort according to the algorithm outlined in Table 1. There will also be up to 40 subjects enrolled into the exploratory dose cohorts to further explore safety, PK, and PD, and approximately 10 subjects enrolled into the 3-week dosing regimen cohort to characterize the PK and safety profile at a 3-week dosing schedule. In Phase 1b, approximately 210 subjects will be enrolled.

 Table 2: DLT evaluation and enrollment decisions will follow the below guidance

 Algorithm for Dose-Escalation Decisions

### 6 STUDY PERIODS, TREATMENT REGIMENS

### 6.1 Study Periods

The study will consist of 3 periods including screening (up to 28 days), treatment, and follow-up. **Screening:** Subjects who have fully consented to participation in the study will undergo screening assessments within 28 days (4 weeks) prior to administration of the first infusion of study treatment.

**Treatment cycles**: (including end of the DLT period and Phase-1a extended treatment period.) For subjects in the monotherapy cohorts: cabiralizumab infusion administered as a 30-minute IV infusion on Day 1 of each 14-day treatment cycle.

For the combination therapy: nivolumab administered first as a 30-minute IV infusion, with a 30to 60-minute rest, followed by a 30-minute infusion of cabiralizumab on Day 1 of each 14-day treatment cycle.

For cohort 1aD (Subjects in 3-week dosing regimen cohort): Study drugs on Day 1 of each 21-day treatment cycle.

**End-of-Treatment Follow-up Period:** All subjects should return to the clinic 28 ( $\pm$ 7) days and 100 ( $\pm$ 7) days from their last dose of study drug to complete the End-of-Treatment Follow-up

Period, irrespective of whether a subject is discontinued from the study drug at a planned visit or mid-cycle. Subjects should continue onto Long-Term Follow-up after completing the End-of-Treatment. Subjects will be followed every 12 ( $\pm 2$ ) weeks for survival, or more frequently as needed.

### 6.2 Treatment Regimens

### Phase 1a Monotherapy Cohorts and Combination Dose Escalation Cohorts (1aM and 1aC)

Phase 1a consists of three cabiralizumab monotherapy cohorts and four dose-escalation cohorts of cabiralizumab in combination with nivolumab with a minimum of 3 subjects enrolled in each cohort. The planned dose levels and schedules for the Phase 1a cohorts are as follows:

- Cohort 1aM1: 2 mg/kg cabiralizumab, every 2 weeks
- Cohort 1aM2: 6 mg/kg cabiralizumab, every 2 weeks
- Cohort 1aM3: 4 mg/kg cabiralizumab, every 2 weeks
- Cohort 1aC1: 1 mg/kg cabiralizumab + 3 mg/kg nivolumab, every 2 weeks
- Cohort 1aC2: 2 mg/kg cabiralizumab + 3 mg/kg nivolumab, every 2 weeks
- Cohort 1aC3: 4 mg/kg cabiralizumab + 3 mg/kg nivolumab, every 2 weeks
- Cohort 1aC4: 6 mg/kg cabiralizumab + 3 mg/kg nivolumab, every 2 weeks

### Phase 1a 3-week Dosing Regimen Cohort (1aD):

4 mg/kg cabiralizumab + 3 mg/kg nivolumab, every 3 weeks (Cohort 1aD1)
 (To characterize the PK profile and safety of cabiralizumab in combination with nivolumab when administered as an alternative dosing schedule.)

### Phase 1a Exploration Cohorts (1aE):

• The Phase 1a exploration consists of up to 40 additional subjects to further evaluate the safety, PK, and PD of cabiralizumab as monotherapy and in combination with nivolumab in melanoma (Cohort 1aE2), anaplastic thyroid cancer (Cohort 1aE3), and pancreatic cancer (Cohort 1aE4).

### Phase 1b Expansion Cohorts:

- Phase 1b will enroll up to 7 expansion cohorts in 6 advanced cancer types (1b1 through 1b7). Enrollment in Phase 1b will begin when an RD has been identified based on overall safety, tolerability, PK, and PD data.
- Cohort 1b1: NSCLC (PD-1 naive)

• Cohort 1b2: NSCLC

(De novo or acquired resistance to anti-PD-1 targeting drug)

- Cohort 1b3: Squamous Cell Carcinoma of the Head and Neck (SCCHN)
- Cohort 1b4: Pancreatic Cancer
- Cohort 1b5: Advanced Ovarian Cancer
- Cohort 1b6: Renal Cell Carcinoma
- Cohort 1b7: Malignant Glioma (GBM)

### 7 STATISTICAL ANALYSES

### 7.1 General Methods

The statistical analysis will be conducted following the principles specified in the International Conference on Harmonisation (ICH) Topic E9 Statistical Principles for Clinical Trials (CPMP/ICH/363/96).

All statistical tabulations and analyses will be done using SAS®, Version 9.3 or higher.

Unless otherwise noted, continuous variables will be summarized using number of non-missing observations (n), arithmetic mean (mean), standard deviation (SD), median, minimum, and maximum; categorical variables will be summarized using the frequency count and the percentage of subjects in each category.

In the data listings, study day relative to first dose of study drug may be presented. Study day relative to first dose will be calculated as: event date – first dose date in the study (+ 1 if event date  $\geq$  first dose date in the study).

When appropriate, baseline is defined as the last non-missing result with a collection date-time less than the date-time of the first dose of study medication. If time is missing, unless otherwise specified, baseline is the last non-missing result prior to or equal to the date of first dose of study drug.

Unless otherwise specified, non-efficacy analyses except for biomarker and PK parameters, will be presented by:

- Overall monotherapy cohorts; overall combination cohorts
- individual or combined cohort by different dose and regimen

For efficacy and biomarker analyses, unless otherwise specified, the summary will be presented by:

- Pancreatic cancer cohort subjects dosed with 4 mg/kg cabiralizumab + 3 mg/kg nivolumab every 2 weeks, i.e., cohort 1aE4+1b4
- Pancreatic 6mg/kg cohort, i.e., cohort 1aC4
- Other individual cohort

PK analyses will be presented by individual or combined cohort by different dose and regimen.

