## Study Design (cont.)

Phase 1a: 3-Week Dosing Regimen	An alternative dosing regimen cohort (1aD) with 10 patients has been added to characterize the PK and safety of cabiralizumab in combination with nivolumab when administered at a 3-week dosing schedule. In this cohort, 4 mg/kg cabiralizumab in combination with 3 mg/kg nivolumab will be administered intravenously every three weeks until disease progression, unacceptable toxicity, or other reason for treatment discontinuation. Patients who enter this cohort will follow eligibility criteria for Phase 1a. Patients will not be evaluated for DLT as the dose frequency is less than Cohort 1aC3 which has cleared the DLT window at the time of this amendment.
Phase 1a: Exploration Cohort	Based on emerging clinical and translational data, up to 40 patients will be included in Phase 1aE to further explore safety, PK, and PD at alternative dose levels or dosing schedules which have already successfully cleared their respective DLT periods. In each cohort, cabiralizumab either as monotherapy or in combination with nivolumab will be administered until disease progression, unacceptable toxicity, or other reason for treatment discontinuation. Patients who enter Phase 1aE will follow eligibility criteria for Phase 1a.
Phase 1b: Dose Expansion	Seven cohorts consisting of approximately 30 patients each in specific tumor types will characterize the safety and evaluate the efficacy at the RD of cabiralizumab in combination with nivolumab. In each cohort, 4 mg/kg cabiralizumab in combination with 3 mg/kg nivolumab will be administered intravenously every 2 weeks until disease progression, unacceptable toxicity, or other reason for treatment discontinuation.

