  - If 2 of the first 6 evaluable patients in a cohort experience a DLT, that cohort will be expanded to 9 evaluable patients.

If the MTD is not reached during the Phase 1a combination dose escalation, or subsequent cycles of treatment in cleared Phase 1a combination cohorts provide additional insight on the safety profile, an RD may be selected based on overall tolerability, safety, PK, and PD (if available).

Sponsor has the option to expand any cohort previously established to be safe in order to obtain additional data or to investigate alternative dose levels to those defined in the protocol. Upon completion of the DLT period, up to 40 additional patients may be enrolled in Phase 1aE to fully characterize safety, PK, and PD.

If a patient in Phase 1a monotherapy does not receive 2 doses of study drug and does not complete safety assessments and if a patient in one of the Phase 1a combination cohorts does not receive 2 doses of each study drug and does not complete the safety assessment (e.g., safety lab and/or AE reporting) in the DLT period for reasons other than drug-related AEs (e.g., disease progression or withdrawal of consent), then an additional patient will be enrolled into the cohort so that the cohort has at least 3 patients evaluable for the DLT period. All such discussions and decisions will be documented as part of the dose escalation decision-making process.

Upon completion of the DLT period, Phase 1a patients may participate in an Extended Treatment Period following the guidelines in Section 3.1.2.2.

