### **3.1.2.5 Phase 1b Expansion Cohorts**

To further characterize safety and efficacy of cabiralizumab in combination with nivolumab, Phase 1b will enroll up to 7 expansion cohorts in 6 advanced cancer types (1b1 through 1b7). Enrollment in Phase 1b will begin when an RD has been identified based on overall safety, tolerability, PK, and PD (if available) data.

During enrollment of any expansion cohort, if the observed number of responses makes it unlikely to achieve a target response rate for that indication, then further recruitment to that cohort may be suspended or terminated.

After initiation of Phase 1b, the dose may be changed based on data from continued dose exploration in Phase 1a. There will be no intra-patient dose modification and any alteration in dose for Phase 1b will only apply to newly enrolled patients in Phase 1b.

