##### **3.2.4.1.2 Cabiralizumab + Nivolumab Combination Cohorts**

###### **Exclusion**

1. Prior exposure to any PD-1 pathway targeting drug
  - a. This will not apply to additional patients enrolled in Phase 1a after completion of the DLT period to fully characterize safety, PK, and PD.
2. Subjects with history of life-threatening toxicity related to prior immune therapy (e.g., anti-CTLA-4 or anti-PD-1/PD-L1 treatment or any other antibody or drug specifically targeting T-cell co-stimulation or immune checkpoint pathways) except those that are unlikely to re-occur with standard countermeasures (e.g., Hormone replacement after adrenal crisis)

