#### Phase 1b

• Efficacy

ORR is defined as the total number of subjects with confirmed responses of either complete response (CR) or partial response (PR) divided by the total number of subjects in the response-evaluable population (as defined in section 7.2) per Response Evaluation Criteria in Solid Tumors, version 1.1 (RECIST v1.1) by investigator assessment

• Safety

- The incidence of adverse events (AEs), serious adverse events (SAEs), clinical laboratory abnormalities, and ECG abnormalities
- The incidence of treatment discontinuations, modifications, and interruptions due to adverse events
- Grade 3 and Grade 4 AEs and clinical laboratory abnormalities

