## 7.5.1 Primary Efficacy

## Summary:

- ORR with corresponding 2-sided 95% CI based on Clopper-Pearson method along with each category of BOR for response-evaluable population based on investigator assessment. Time to response will be also included.
- ORR with corresponding 2-sided 95% CI based on Clopper-Pearson method along with each category of BOR for safety population based on investigator assessment.

ORR is defined as total number of subjects with confirmed responses of either CR or PR divided by the total number of subjects in the respective population per RECIST v1.1 by investigator assessment. Time to response will be also included.

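### SAP 7.1 shows pancreatic cohort 1b4 only pooled with 1aE4, so the Phase 1b primary endpoint (ORR) has no planned estimate or confidence interval for 1b4 itself

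*SAP*

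**What the plan says.** SAP 7.1 gives a default grouping for all efficacy and biomarker summaries, which applies unless another grouping is specified. It has three lines:

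1. "Pancreatic cancer cohort subjects dosed with 4 mg/kg cabiralizumab + 3 mg/kg nivolumab every 2 weeks, i.e., cohort 1aE4+1b4";
2. the pancreatic 6 mg/kg cohort, 1aC4;
3. a residual line for the other cohorts, each shown individually.

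SAP 4.1 and Protocol 7.3.2.1 make confirmed ORR by investigator assessment a Phase 1b primary endpoint. SAP 7.5.1 tabulates it with a two-sided 95% Clopper-Pearson interval, "along with each category of BOR for response-evaluable population based on investigator assessment", and again for the safety population. SAP 7.5.2 repeats both for central review. These sections fix the population, the assessor and the interval method. They do not fix a cohort or phase split.

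The two pooled cohorts are described differently. SAP 6.2 says "The Phase 1a exploration consists of up to 40 additional subjects to further evaluate the safety, PK, and PD of cabiralizumab" and names 1aE4 as the pancreatic exploration cohort. Protocol 3.1.2.5 says "To further characterize safety and efficacy of cabiralizumab in combination with nivolumab, Phase 1b will enroll up to 7 expansion cohorts", of which 1b4 is one.

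**The concern.** Phase 1b is built cohort by cohort. Each cohort has about 30 patients and its own eligibility section, and Protocol 3.1.2.5 allows recruitment to a single cohort to stop on its observed responses. Patients enter either Phase 1a or Phase 1b. For pancreatic cancer at the Phase 1b regimen, however, the only planned ORR combines patients from both phases.

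That would matter little if the two groups were admitted on the same terms, but on paper they are not. If 1aE4 patients differ in prior immunotherapy or disease burden, the pooled rate describes a population that neither cohort defines. The study is descriptive, so the planned estimate and its interval are the result. No hypothesis test stands beside them.

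**Working it through.** **1. Does any later section restore 1b4?** The 7.1 default gives way only where another grouping is specified.

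| SAP section | What it adds | 1b4-only ORR? |
|---|---|---|
| 7.5 | BOR rules, populations, assessors; PFS and OS by prior lines in pancreatic patients | No |
| 7.5.1 | ORR by investigator, two populations | No |
| 7.5.2 | OS, PFS, DOR; ORR by central review, two populations; figures; listings | No |

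Because 1b4 is named in the first line of the default list, the residual line does not ordinarily pick it up again. The other six Phase 1b cohorts do keep individual summaries.

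**2. Are the pooled cohorts admitted on the same terms?**

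- *Governing criteria.* The Protocol synopsis states: "Patients who enter Phase 1aE will follow eligibility criteria for Phase 1a". Cohort 1b4 has its own section, 3.2.4.2.4.
- *Prior PD-1 therapy.* Protocol 3.2.4.1.2 excludes it for Phase 1a combination patients, then adds: "This will not apply to additional patients enrolled in Phase 1a after completion of the DLT period to fully characterize safety, PK, and PD". Protocol 3.1.2.1 describes the exploration patients in matching terms: "up to 40 additional patients may be enrolled in Phase 1aE to fully characterize safety, PK, and PD". The waiver therefore appears to cover 1aE4. Cohort 1b4 excludes prior immune cell-modulating antibodies.
- *Other 1b4 rules.* It requires adenocarcinoma and excludes other pancreatic primaries, active pancreatitis and ascites of Grade 2 or higher. None of these is stated for Phase 1a.
- *Shared rule.* The albumin threshold for pancreatic patients is in the criteria for all cohorts, so it does not separate them.

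**3. The plan's own enrolment figures (SAP 2.1, Protocol 3.2.1).**

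- Phase 1b: 7 × 30 = 210, as stated.
- Phase 1a: 20 + 15 + 10 + 40 = 85, as stated.
- Total: 85 + 210 = 295, as stated.

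No null rate, target rate or power is given, so there is nothing further to reproduce.

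**4. Size of 1aE4.** It is not stated. Protocol 4.4 describes six exploration cohorts of about 10, which implies 6 × 10 = 60. This conflicts with the cap of 40 in Protocol 3.1.2.4 and 3.2.1 and SAP 6.2. I take 10 as a working assumption.

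- Share of the pool with 10 in 1aE4: 10/(30 + 10) = 25.0%.
- Upper bound, if 1aE4 used the whole cap: 40/(30 + 40) = 57.1%. This is not realistic, because the cap is shared with at least 1aE2 and 1aE3.

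**5. Illustration with exact intervals.** For x responders among n, the 95% Clopper-Pearson limits are the 0.025 quantile of Beta(x, n − x + 1) and the 0.975 quantile of Beta(x + 1, n − x). All responder counts are assumed, and 30 is the enrolment target, not a known evaluable count.

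| Group | x/n | ORR | 95% CI | Shift from 1b4 |
|---|---|---|---|---|
| 1b4 alone | 4/30 | 13.3% | 3.8 to 30.7 | – |
| Pool, 0/10 in 1aE4 | 4/40 | 10.0% | 2.8 to 23.7 | 10.0 − 13.3 = −3.3 |
| Pool, 2/10 in 1aE4 | 6/40 | 15.0% | 5.7 to 29.8 | 15.0 − 13.3 = +1.7 |
| Pool, 3/10 in 1aE4 | 7/40 | 17.5% | 7.3 to 32.8 | 17.5 − 13.3 = +4.2 |

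**6. The reverse question.** Suppose the report shows a pooled 4/40 = 10.0%. With 10 patients in 1aE4, cohort 1b4 could have had anything from 0/30 (0%, CI 0 to 11.6) to 4/30 (13.3%, CI 3.8 to 30.7). The pooled figure does not identify the 1b4 figure.

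**The case against.** The strongest counter-argument is that no text promises an ORR for 1b4 alone. The endpoint definitions name no cohort, and Protocol 7.4.2 summarises ORR by disease type. Pooling one disease on one regimen, with 6 mg/kg kept apart, is close to that rule. This gives the pool real support, but it does not settle the matter. Protocol 7.4.2 does not say that Phase 1a patients belong in a Phase 1b primary endpoint. The SAP also does not follow it elsewhere: 1b1 and 1b2 are both NSCLC and are shown separately.

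Second, the residual line in SAP 7.1 is terse, and SAP 7.3.2 treats the pool as an extra display for demographics. A programmer might therefore show 1b4 anyway. That is possible, but the 7.3.2 wording is confined to demographics, and an ambiguity about a primary endpoint is itself worth removing.

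Third, the differences between the cohorts are unproven. The documents do not show that any 1aE4 patient would fail a 1b4 criterion. The Protocol never defines 1aE4 individually, and applying the PD-1 waiver to it is an inference from matching wording. SAP 7.3.2 and Appendix 2 also display baseline ascites and albumin for pancreatic patients by individual cohort, so some differences would be visible. All of this stands and limits what can be claimed. The biopsy requirements also differ between the cohorts, but nothing links that to response, so I give it no weight.

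Fourth, analyses are descriptive, no formal interim analysis is planned, and the listings in SAP 7.5.2 include each patient's BOR. A reader with the listings could therefore rebuild the 1b4 rate. That lowers the stakes, but a listing is not a planned estimate with an interval.

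**Conclusion.** The point holds. Followed as written, the SAP reports the Phase 1b primary efficacy endpoint for pancreatic cancer only as a mix of Phase 1a and Phase 1b patients. One of seven Phase 1b cohorts is affected.

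The numerical effect cannot be known from the documents. In the illustration it runs from −3.3 to +4.2 points, inside the 1b4 interval of 3.8 to 30.7. That range rests on assumed responder counts, 30 patients in 1b4 and 10 in 1aE4. No bias is shown in either direction. The gap should be corrected, but it does not threaten the study: the data are collected and the estimate is recoverable.

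**What to change.** In SAP 7.1, add cohort 1b4 alone to the efficacy display groups. SAP 7.5.1 and 7.5.2 would then report its ORR with a Clopper-Pearson interval as the Phase 1b pancreatic result, and DOR, PFS and OS would follow the same grouping. Keep 1aE4+1b4 as a labelled supportive pool and state the number of patients from 1aE4. SAP 7.3.2 already uses a layout of individual cohort plus overall within tumour type for baseline disease characteristics, and efficacy can follow it. State also how this fits with the disease-type wording in Protocol 7.4.2.

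The cost is SAP wording and one extra column per efficacy table. For ORR that means four tables (two assessors in two populations), plus those for DOR, PFS and OS. No new data are needed. The drawback is a wider interval for 1b4 alone. For example, 4/30 has a width of 27.0 points, against 22.6 points for a pooled 5/40 (4.2 to 26.8).

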### 7.2 Study Population

- Enrolled Population: All subjects who signed the ICF and are approved for enrollment with a study subject number assigned by sponsor or designee.
- Response-Evaluable Population based on investigator assessment: Subjects who have a measurable lesion at baseline and one of the following: 1) at least 1 post-baseline tumor assessment, 2) clinical progression, 3) death.
- Response-Evaluable Population based on central review assessment: Subjects who have one of the following: 1) at least 1 post-baseline tumor assessment, 2) clinical progression, 3) death.
- Safety Population: All subjects who receive any dose of cabiralizumab and/or nivolumab. This is the population of primary interest for the summaries of demographics, baseline characteristics, prior therapy, exposure, and safety. Summaries of OS, PFS, and ORR will also be provided for this population.
- PK Concentration Population: All subjects who receive at least one dose of cabiralizumab and/or nivolumab and have at least one available serum concentration data.
- PK Evaluable Population: Subjects in the PK Concentration Population who have adequate PK assessments to reliably derive at least one PK parameter. This is the population of primary interest for the summaries of the PK parameters and exploratory analyses of the association of PK data with efficacy measures.
- Biomarker Subjects: All subjects who receive at least one dose of cabiralizumab and/or nivolumab and have available biomarker data.
- Immunogenicity Subjects: All subjects who receive at least one dose of cabiralizumab and/or nivolumab and have available ADA data.

### 7.3 Study Conduct

## 7.3.1 Subject Disposition

Summary 1:

Number (%) of subjects will be presented for the following analysis population:

- Enrolled population
- Safety population
- Response-Evaluable population
- PK concentration population
- PK Evaluable population
- Biomarker subjects
- Immunogenicity subjects

The number of enrolled subjects will serve as the denominator for the percentage calculation.

#### Summary 2:

Subject disposition will be presented for enrolled population. Number (%) of subjects will be presented for the following:

- Enrolled in study
- Received treatment (yes/no)
- Discontinued from treatment
- Reason for treatment discontinuation
- Discontinued from study
- Reason for study discontinuation
- Participated in long-term follow-up (yes/no)

Denominator for 'Received treatment (yes/no)' will be based on the number of enrolled subjects. For all others, percentages will be based on the number of subjects in safety population.

Summary 3:

Number (%) of enrolled subjects who have specified protocol deviation and summary for a given category or subcategory of the protocol deviation.

Listing:

- Analysis population and subject disposition for each enrolled subject.
- Subjects with protocol deviations

### 7.3.2 Demographics and Baseline Disease Characteristics

#### Summary:

- Descriptive summary statistics will be provided for the safety population. The included demographic characteristics are: age, sex, race, and ethnicity. Two age categories in years will be summarized: <65, 65-85, >=85, or <65, 65-75, >=75. Additionally, summary for pancreatic cancer cohort subjects dosed with 4 mg/kg cabiralizumab + 3 mg/kg nivolumab every 2 weeks, i.e., cohort 1aE4+1b4, will be included along with other cohorts specified in section 7.1. Descriptive statistics of baseline physical measurements will be provided for safety population. Included measurements are height, weight, and ECOG performance status.
- Descriptive statistics of baseline disease characteristics for safety population by tumor type, associated individual cohort and overall within the given tumor type.
- Descriptive statistics of selected baseline disease characteristics for safety population with Melanoma.
- Descriptive statistics of selected baseline disease characteristics for safety population with NSCLC.
- Descriptive statistics of selected baseline disease characteristics for safety population with ovarian cancer.
- Descriptive statistics of selected baseline disease characteristics for safety population with SCCHN.
- Descriptive statistics of selected baseline disease characteristics for safety population with pancreatic cancer.
- Descriptive statistics of selected baseline disease characteristics for safety population with RCC.
- Descriptive statistics of selected baseline disease characteristics for safety population with GBM.

Please refer to Appendix 2 for the baseline disease characteristics summarized for different tumor type.

